### 3.1.5 Censoring and Non-Protocol Graft Failures

#### 3.1.5.1 Eyes with Incomplete Follow-Up

In eyes that dropped prior to the 3 year visit without meeting criteria for graft failure the following ‘rules’ will apply:

1. A cornea that is “on the path to failure” (per 3.1.4 above) at the last completed visit AND was cloudy at least once during the “on the path to failure” period will be flagged for **‘non-protocol’ graft failure review by the Executive Committee**. If confirmed as a non-protocol graft failure, the failure date will be determined as it is in 3.1.4 above.
2. All others *will NOT* be considered a graft failure and the data will be **censored** at the last completed visit

#### 3.1.5.2 Eyes with 3 Year Visit Not Meeting Failure Criteria

In eyes that complete the 3 year visit without meeting criteria for graft failure the following ‘rules’ will apply:

1. If the cornea is “on the path to failure” (per 3.1.4 above) at the 3 year visit, data beyond the 3 year visit up to 42 months will be used (if available) to determine whether the cornea will be considered a failure up to 3 years. Data beyond 42 months will not be used for this assessment.
  - If the cornea clears at a subsequent follow-up visit (within 42 months) prior to meeting confirmation of failure criteria, the cornea will not be classified as a graft failure and data will be censored at the 3 year visit.
  - If additional follow-up data (within 42 months) confirm a failure (via regraft or 90 days confirmed cloudy), then the cornea will be classified as a graft failure up to 3 years and date of failure will be determined per 3.1.4 above.
  - If data beyond the 3 year visit are not available, OR the cornea remains “on the path to failure” beyond the 3 year visit but the follow-up data that are available within 42 months still do not confirm failure, the case will be flagged for **‘non-protocol’ graft failure review by the Executive Committee**. (Note all of these cases will have been cloudy at least once during the “on the path to failure” period.) If confirmed as a non-protocol graft failure, the failure date will be determined per 3.1.4 above.
2. If the cornea is not “on the path to failure” (clear or equivocal following clear) at the 3 year visit, it *will NOT* be considered a graft failure and the data will be **censored** at the 3 year visit

#### 3.1.5.3 Severe Events Unrelated to Preservation Time

In eyes that met failure due to a severe event unrelated to preservation time (listed in section 3.1.2.1), the following ‘rules’ will apply:

1. A cornea that is “on the path to failure” (per 3.1.4 above) at the last completed visit prior to the severe event leading to failure AND was cloudy at least once during that “on the path to failure” period prior to

257  
258  
259  
260  
261  
262  
263  
264  
265  
266  
267  
268  
269  
270  
271  
272  
273  
274  
275  
276  
277  
278  
279  
280  
281  
282  
283  
284  
285  
286  
287  
288  
289  
290  
291  
292  
293  
294  
295  
296  
297  
298  
299  
300  
301  
302  
303  
304  
305  
306  
307  
308  
309  
310  
311  
312

the event will be flagged for '**non-protocol' graft failure review by the Executive Committee**. If confirmed as a non-protocol graft failure, the failure date will be determined as it is in 3.1.4 above.

2. All others *will NOT* be considered a graft failure and the data will be **censored** at the last completed visit prior to the severe event leading to failure.

Examples

Example 1  
clear  
clear  
cloudy                    ← 'non-protocol' failure date  
equivocal  
lost to followup

Example 2  
clear  
clear  
equivocal  
equivocal                    ← censored date  
lost to followup

Example 3  
clear  
clear  
cloudy                    ← 'non-protocol' failure date  
blunt trauma  
cloudy  
regraft

Example 4  
clear  
cloudy  
clear                    ← censored date  
blunt trauma  
cloudy  
regraft

Example 5  
equivocal (1 day)  
equivocal                    ← censored date  
lost to followup

Example 6  
equivocal (1 day) ← 'non-protocol' failure date  
cloudy  
lost to followup

### 3.1.6 Clarifications Regarding 3 Year Visit Windows

The visit that the site designates as the "3 year visit" is the one that drives whether a 3 year failure has occurred. If the eye is dropped without meeting failure and prior to completion of the 3 year visit, the rules in 3.1.5.1 apply. If failure definition is met prior to a 3 year visit, then this is counted as a 3 year failure according to 3.1.4. If failure is not met prior to a 3 year visit, the rules in 3.1.5.2 are followed. The following clarifications regarding visit windows will apply to these rules:

- The window for the 3 year visit, per protocol, is 35-42 months. The 3 year visit will be permitted to occur late out of window, up to 44 months. For a 3 year visit occurring late out of window (between 42-44 months) the same rules above apply relative to this designated 3 year visit.
- If there is no designated 3 year visit completed, data (i.e. unspecified visits) up to 44 months can be used to determine if failure met. The same rules above will apply.
- NOTE: This means that data beyond 42 months (up to 44 months) CAN be used to determine 3 year failure status if and only if the visits occur prior to or including a designated 3 year visit late out of window, OR in the absence of a designated 3 year visit.

### 3.1.7 Unadjusted Analysis

Three year Kaplan-Meier graft failure estimates with 95% confidence intervals (variance estimated using the Greenwood method) will be calculated separately for the two treatment groups ( $\leq 7$  days and 8 to 14 days from preservation to surgery). A one-sided 95% confidence interval will be constructed for the difference in 3 year graft failure rates between the two groups. The bootstrap re-sampling technique will be used to account for potentially correlated data from donors who donated both corneas in this study and potentially correlated data from 2 study eyes of the same study participant. The technique will sample with replacement from the observed dataset. For each bootstrap sample the effect of preservation time will be estimated using the same method as in the primary analysis. Confidence intervals will be calculated using the bias-corrected and accelerated method. The number of bootstraps will be 100,000.

The two treatment groups will be declared equivalent if the one-sided 95% confidence interval for the difference in proportions excludes the pre-defined non-inferiority limit of 4%.

### 3.1.8 Adjusted Analysis

Multivariate analysis will be performed using Cox proportional hazards regression model. The primary multivariate model will include the corneal diagnosis regardless of statistical significance, in addition to time from preservation to surgery (treated as a binary variable).

In additional models, potential confounders including recipient and donor age, recipient and donor race, presence of glaucoma, presence of corneal vessels, history of smoking, and certain aspects of the retrieval and processing of the donor tissue (including multiple types of storage media, if more than one is used in preservation of the corneal tissues, observations during or after cutting, time from cut to surgery, and donor rim culture results) will be screened by assessing the change in the preservation time effect when the potential confounder is controlled for in the Cox model. Univariate models will be evaluated first, and factors from those models with a p value  $<0.10$  will then be evaluated in a multivariate model. A final model will be constructed consisting of factors with a p value  $<0.01$  following a backwards selection process.

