### 3.1.9 Surgeon Effect

363  
364  
365  
366  
367 Random surgeon effects will be tested using a generalized linear model via the SAS  
368 GLIMMIX procedure. This marginal model produces a robust standard error (RSE)  
369 by use of a sandwich estimator, which corrects for correlated data.  
370  
371  
372  
373  
374  
375  
376

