### 3.1.10 Analysis of Potential Interaction

377 Potential effect modifiers of donor tissue preservation time such as recipient age or  
378 corneal diagnosis will be screened by including first-order interaction terms.  
379 Variables that exhibit modification of the donor tissue preservation time effect with  
380 an associated P value  $< 0.10$  will be added to the model, and the final model will be  
381 constructed consisting of terms with a p value  $< 0.01$  following a backwards selection  
382 process.  
383  
384  
385  
386

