## 3.2 Secondary Analyses of 3 Year Graft Failure

### 3.2.1 Preservation Time

387 The time from preservation to surgery is treated as a binary variable in the primary  
388 analysis (see above section). Secondary analyses will look at the time from  
389 preservation to surgery as a categorical variable with multiple levels and as a  
390 continuous variable:

- 391 • Kaplan-Meier estimates of graft failure with 95% confidence interval will be  
392 calculated for each of the following groups: 0 – 4, 5 – 7, 8 – 11, and 12 – 14 days  
393 from preservation to surgery (counting partial days as whole days).
- 394 • A Cox proportional hazards model will be constructed treating the time from  
395 preservation to surgery as a continuous variable (using time of day to calculate  
396 hours from preservation to surgery). Polynomial terms will be added to assess any  
397 curvilinear, J, or U shaped relationship between time from preservation to surgery  
398 and graft failure. If no significant departure from a linear relation is detected, a  
399 one sided 95% confidence interval will be computed for the hazard ratio per day  
400 of time from preservation to surgery.
  - 401 ▪ The proportional hazards assumptions will be tested through the use of time-  
402 dependent variables with a logarithm transformation of time. If this  
403 assumption is violated then hazard ratios will be presented separately for  
404 different periods following transplant.

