### 3.2.2 Predictive Factors – (*Analysis plan for objective 3, graft failure outcome*)

405 The association of factors potentially related to graft failure will be evaluated in  
406 univariate and multivariate Cox models, adjusting for preservation time group  
407 regardless of statistical significance. The proportional hazards assumptions will be  
408 tested as described above. Univariate models will be evaluated first, and factors from  
409 those models with a p value  $< 0.10$  will then be evaluated in a multivariate model. A  
410 final model will be constructed consisting of factors with a p value  $< 0.01$  following a  
411 backwards selection process.

412 Potential factors to evaluate include:

- 413 • Recipient factors
  - 414 ➤ preoperative diagnosis

411                   ➤ gender  
412                   ➤ age  
413                   ➤ race  
414                   ➤ prior use of glaucoma medication  
415                   ➤ prior glaucoma surgery (trabeculectomy, laser procedure)  
416                   ➤ current smoker (at time of surgery)  
417                   ➤ lens status (phakic, posterior chamber intraocular lens)  
418                   ➤ Intraocular pressure (IOP)  
419

420                   • Donor/graft factors  
421                   ➤ eye bank determined screening ECD  
422                   ➤ pre-operative CIARC determined ECD  
423                   ➤ age  
424                   ➤ gender  
425                   ➤ race  
426                   ➤ history of diabetes  
427                   ➤ cause of death  
428                   ➤ type of storage medium  
429                   ➤ death to preservation time  
430                   ➤ surgeon cut vs eye bank cut  
431                   ➤ postcut thickness  
432                   ➤ cut to surgery time  
433                   ➤ observations during or after cutting  
434

435                   • Surgical factors  
436                   ➤ Insertion method  
437                   ➤ Incision location  
438                   ➤ Incision site  
439                   ➤ Graft size  
440

441                   • Postoperative factors  
442                   ➤ Dislocation  
443                   ➤ Rebubbling  
444                   ➤ IOP  
445                   ➤ Graft rejection  
446                   ➤ Corneal thickness  
447  
448

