### 3.2.3 ECD as Time Dependent Predictor of Graft Failure

The relationship between endothelial graft failure (graft failure due to endothelial decompensation) and ECD will be addressed paralleling the methods used in the CDS. A Cox model will be fit with ECD as a time dependant covariate. This analysis will be limited to subjects with at least one gradable follow up image. The rate of change will also be calculated as a time dependent variable defined as the least squares slope over all previous measurements starting at 6 months (e.g., the rate of change at one year would be the slope fit to the 6 month and 1 year ECD values). Missing values will be imputed by Rubin's method. If non-linear effects are detected, transformations will be used. For ease of interpretation, results will be presented as discrete categories with cutpoints chosen to display the trends identified from the transformed model. P-

460 values will still be from a continuous analysis although data are displayed as  
461 categories. The proportional hazards assumptions will be tested as described above.  
462

463 To check whether results are sensitive to how missing data are handled, a second  
464 model will be fit with a time dependent indicator for missing ECD.  
465

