### 466 3.2.4 Secondary Outcome of Graft Rejection

467 Associations of baseline recipient and donor factors with the occurrence of a graft  
468 rejection will be assessed in univariate and multivariate proportional hazards models.  
469 Life-table analyses will be used to compute the probability of a first rejection event  
470 within intervals defined by the study exam schedule. Data will be censored at the time  
471 of a non-rejection graft failure or at the last visit.

472 A Kaplan-Meier approach will be considered for evaluating probability of first graft  
473 rejection, and time dependency of repeated rejection events will also be explored.  
474 Determination of the timing of a separate episode graft rejection will include a  
475 confirmation that the eye was off steroids at the visit where rejection was reported.  
476

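### Five SAP sections with Cox or proportional hazards models, and the pre-operative ECD model, state no handling of the fellow-eye and mate-cornea correlation that the SAP allows for elsewhere

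*Combined protocol and SAP*

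**What the plan says.** Protocol 2.6 lets a participant enrol both eyes; the first is randomised and the second goes to the other preservation-time group. One donor may also supply both corneas to the study.

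The SAP allows for both kinds of link in two places. In 3.1.7, for the difference in 3-year failure rates, "The bootstrap re-sampling technique will be used to account for potentially correlated data from donors who donated both corneas in this study", and the same sentence adds two study eyes of one participant. In 4.1.4, the 3-year ECD model has random effects for the same two sources, and 4.2.1 repeats those analyses.

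The other time-to-event models are stated without it:

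- 3.1.8, adjusted effect: "Multivariate analysis will be performed using Cox proportional hazards regression model".
- 3.1.10, interactions: "Potential effect modifiers of donor tissue preservation time such as recipient age or" corneal diagnosis are screened through interaction terms.
- 3.2.1, continuous preservation time: if the relation is linear, a "one sided 95% confidence interval will be computed for the hazard ratio per day".
- 3.2.2, Objective 3: "univariate and multivariate Cox models, adjusting for preservation time group", with a p<0.10 screen and then p<0.01 to stay in the model.
- 3.2.4, rejection: associations with "rejection will be assessed in univariate and multivariate proportional hazards models".

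Section 4.3 (pre-operative ECD) is a plain ANCOVA. The only other mention of correlation is in 3.1.9, where a GLIMMIX model for surgeon effects gets its standard error "by use of a sandwich estimator, which corrects for correlated data". Section 8.3 carries the 3-year methods for the three objectives to years 4 and 5.

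**The concern.** A standard Cox fit treats every eye as independent. If linked eyes have positively correlated outcomes, its standard errors are wrong, and the direction depends on the covariate.

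A factor that is the same for both eyes of a participant (age, gender, race, smoking), or for both corneas of a donor (age, gender, race, diabetes, cause of death), carries less information than the number of eyes suggests. Its standard error is too small. Objective 3 is one of the three stated objectives, and 3.2.2 selects such factors by p-value.

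Preservation time is different. The two eyes of a participant are in opposite groups, so the comparison is partly within-person and the independence standard error is too large. Interaction terms between preservation time and a recipient factor tend the same way. Intervals such as the one-sided interval per day in 3.2.1 would then not have their stated coverage. If the variance method is left open, it can also be chosen after the data are seen.

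**Working it through.** **The plan's own figure.** SAP 2.0 assumes 6% failure in both groups, a 4-point limit, one-sided 5% and 90% power. Per group: 2 × 0.06 × 0.94 × (1.645 + 1.282)² / 0.04² = 603.8, so 604, or 1208 in total. Then 1208 × 1.10 = 1328.8, which agrees with 1330. The SAP says this leaves out the two-eye correlation, because its size is not known. No sample-size figure is in dispute.

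**Assumptions (not in the documents).** Let f be the share of eyes in two-eye pairs and ρ the fellow-eye correlation of failure. I take f = 0.2-0.4 and ρ = 0.2-0.5. The top end is extreme: at 6% failure and ρ = 0.5, the fellow of a failed eye would fail with probability 0.06 + 0.5 × 0.94 = 53%.

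**Formulas (true variance / variance used, V).**

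- Factor shared by both eyes: V = 1 + fρ.
- Preservation-time arm, eyes in opposite groups: V = 1 − fρ.
- Preservation time in days, taken as spread evenly over 0-7 and 8-14: the between-group variance is (7.5/2)² = 14.06 and the average within-group variance is (5.25 + 4.00)/2 = 4.63. The within-pair correlation of days is therefore −14.06/18.69 = −0.75, and V = 1 − 0.75fρ.
- The true level is the normal tail area beyond z/√V, where z is the nominal critical value.

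| f, ρ | V shared | 1% rule | 10% screen | V arm | Arm, one-sided 5% | Days, one-sided 5% |
|---|---|---|---|---|---|---|
| 0.2, 0.2 | 1.04 | 1.15% | 10.7% | 0.96 | 4.66% | 4.7% |
| 0.4, 0.3 | 1.12 | 1.49% | 12.0% | 0.88 | 3.98% | 4.2% |
| 0.4, 0.5 | 1.20 | 1.87% | 13.3% | 0.80 | 3.30% | 3.7% |

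**Check by simulation.** The set-up was 1330 eyes, 6% failure, 10% loss and no true effects, with a Cox score test that ignores the links, in the same three settings.

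- Mixture model, 60,000 runs: shared factor at the 1% rule 1.18%, 1.51%, 1.89%; arm 4.73%, 4.05%, 3.34%; days 4.85%, 4.32%, 3.76%.
- Gaussian copula, 40,000 runs: shared factor 1.18%, 1.48%, 1.74%; arm 4.80%, 4.05%, 3.25%; days 4.83%, 4.24%, 3.61%.

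Both agree closely with the formulas.

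**Size for Objective 3.** For the four plainly shared recipient factors, the extra expected false selections are 4 × (0.15 to 0.87 points) = 0.006 to 0.035. Donor-level factors move the same way, but the documents give no share of mate corneas to size them.

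**Crossovers.** SAP 3.1.2.2 analyses wrong-group eyes as treated. If a share c of pairs ends in one group, V for the arm is 1 − fρ(1 − 2c). With c = 5%, 0.80 becomes 0.82.

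**Mate corneas and the arm effect.** Let g be the share of corneas with a mate in the study and r the mate correlation, both assumed. Then V = 1 − fρ + gr if mates share a group, and 1 − fρ − gr if they are in opposite groups.

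| f, ρ, g, r | Mates | V | Formula | Simulated (40,000 runs) |
|---|---|---|---|---|
| 0.2, 0.2, 0.4, 0.3 | same group | 1.08 | 5.67% | 5.77% |
| 0.2, 0.2, 0.4, 0.3 | opposite | 0.84 | 3.64% | 3.62% |
| 0.4, 0.3, 0.2, 0.2 | same group | 0.92 | 4.32% | 4.50% |
| 0.4, 0.3, 0.2, 0.2 | opposite | 0.84 | 3.64% | 3.79% |

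Only the first row exceeds 5%. A reversal needs mates in the same group and gr larger than fρ.

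**The case against.** The strongest reply is that the SAP is silent here and does not state that eyes are independent. It names both sources of correlation in 3.1.7 and 4.1.4, so the authors knew of them. In the protocol the sandwich-variance bullet sits under the same heading as the Cox model (7.2.1.2). The effect is also small. SAP 3.2.2 lists 31 candidate factors; if all were null and independent, a 1% rule would itself admit about 0.3. The SAP also tightened retention to p<0.01 from the p<0.05 in protocol 7.2.2.2, and 1.2-1.9% is still well inside the protocol's threshold. No margin or decision rule hangs on any of these models.

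The points on size and awareness stand, and they keep the severity low. They do not fill the gap. The sandwich estimator belongs to the GLIMMIX surgeon model and names neither participant nor donor as the cluster. Nothing in the listed Cox sections or in 4.3 refers back to the bootstrap or the random effects.

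A second objection also stands. Section 3.2.3 says "A Cox model will be fit with ECD as a time dependant covariate", but it follows the methods of the earlier donor study, which are not in the documents, and ECD is measured per eye. A reader might count 3.2.3 as a further error; the documents do not allow that.

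**Conclusion.** Wrong as written for the error bars, and of low severity. In 3.1.8, 3.1.10, 3.2.1, 3.2.2 and 3.2.4, and in the 4.3 ANCOVA, the stated models leave out a correlation that the SAP accounts for elsewhere.

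With 20-40% of eyes paired and correlation 0.2-0.5, the 1% rule for shared recipient factors runs at about 1.2-1.9% and the 10% screen at 10.7-13.3%. From fellow-eye correlation alone, a one-sided 5% test runs at about 3.3-4.7% for the binary arm and about 3.6-4.8% per day.

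Three stronger readings are not supported:

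- That the non-inferiority conclusion is at risk. That decision rests on the 3.1.7 bootstrap, whose stated purpose is to cover both links.
- That the preservation-time results are anti-conservative. Fellow-eye correlation works the other way. Mate corneas could offset or reverse it only under the conditions shown in the working, and the documents do not say how mates are allocated or how strongly they correlate.
- That 3.1.7 resamples single eyes, or that 4.2.2 and 4.2.3 ignore the links. The resampling unit is unnamed, and it is unclear whether the 4.1.4 random effects carry over. These are requests for clarification.

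**What to change.** - **3.1.8, 3.1.10, 3.2.1, 3.2.2, 3.2.4:** state that standard errors use a robust (sandwich) variance clustered on sets of eyes linked by a shared participant or donor. If the links chain into large sets, use two-way participant and donor clustering.
- **3.2.3:** apply the same variance unless the earlier study's methods already do.
- **4.3:** add a donor random effect. The outcome is measured on the donor cornea before transplantation, so a participant effect is not needed.
- **8.3:** carry the same wording to the 4- and 5-year analyses.
- **Clarifications only:** say that the 4.1.4 random effects apply in 4.2.2 and 4.2.3, and that the 3.1.7 bootstrap, including the jackknife step of its bias-corrected and accelerated interval, resamples linked sets and not single eyes.

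The cost is a few sentences, a standard software option and a little more analysis work. No new data are needed.

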### 3.1.2 Assignment of Donor to Study Eyes

545 The primary eye bank, as designated by the clinical site, will receive a notification when there is  
546 a pending donor assignment. The Eye Bank Procedures Manual provides details regarding the  
547 assignment process. When the eye bank submits an assignment request, a computer program  
548 will use a minimization algorithm to evaluate all available donors and ensure a balance of  
549 subgroups (0-4 days, 5-7 days, 8-11 days, 12-14 days from preservation to surgery) within the  
550 primary randomization groups. Time from preservation to scheduled surgery date will be  
551 calculated as whole days for the purpose of assignment into the appropriate randomized  
552 preservation time group. As surgeons will be masked to all donor information, the label and  
553 report that accompanies the donor will be generated from the study website in such a way to  
554 maintain masking.

556 After the donor assignment procedure is completed, the eye bank will complete a donor  
557 information form on the study website, which includes information about the retrieval of the  
558 cornea (date/time of death, date/time of retrieval, aspects of the processing), cause of death, age  
559 of the donor, and ECD.

560

561 For those assignments where pre-cut tissue has been requested, the eye bank will cut and prepare  
562 the tissue on the same day that they would cut tissue if the donor was being assigned to a non-  
563 study participant for that particular surgeon, and will complete a cutting information form.

564

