688 technician(s) performing this procedure will be certified by the CIARC.

689 **4.6 Additional procedures**

690 Data on all additional procedures performed on the study eye will be collected, including:

691 • air bubbling/repositioning in the first month  
692 • cataract surgery and placement of intraocular lens (anterior chamber, posterior chamber)  
693 • YAG capsulotomy

694       • refractive procedure (e.g. limbal relaxing incision, LASIK)  
695       • glaucoma surgery (e.g. trabeculectomy, laser trabeculoplasty, tube shunt, mini-shunt, other)

696       Additionally, data on donor tissue rim cultures may be collected if performed as part of standard  
697       of care.

698

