## 7.1 Sample Size

The sample size of 1330 is calculated based on a non-inferiority (a single one-sided test) design with the goal to determine that the graft failure rate of the recipients of donor tissue transplanted 8 to 14 days after preservation is not worse than the graft failure rate of recipients of donor tissue transplanted  $\leq 7$  days after preservation.

Non-Inferiority Limit	Power = 90%				
	Failure Rate				
	12%	10%	8% a	6%	4%
10%	362	310			
8%	566	482	394		
6%	1006	858	702	538	
4 %	2262	1928	1576	1208	824
2%	9044	7708	6304	4832	3290

Note: Numbers in table are total sample size for both treatment groups combined (crossover and lost to follow up are not accounted for). Half would be randomized to each group.

a CDS data: 3-year failure rate

In the Cornea Donor Study (CDS), the 3-year failure rate was 8%. Clinical expectations suggest that the graft failure rate from the EK procedure will be smaller than the failure rate from the PKP procedure that was used in CDS; therefore, a 3-year failure rate of 6% has been assumed. Based on equal allocation of recipients to each group and type I error of 5%, a sample size of 1208 will provide 90% power for a non-inferiority limit of 4%. Based on information from the CDS, approximately 10% of subjects will have incomplete follow up (due to death, withdrawal or lost to follow up) by the end of year 3. Increasing the calculated sample size by this amount gives a total of 1330 subjects (665 per group).

- The inclusion of participants with two study eyes, one in each treatment group, will tend to reduce the variance and as a result increase statistical power. To be conservative, this has not been accounted for in the sample size estimation, since the correlation of outcome with two eyes is not known.

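### The additional adjusted models in SAP 3.1.8 treat variables that longer storage may itself change as confounders of the preservation-time effect, so they can understate harm

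*Combined protocol and SAP*

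**What the plan says.** SAP 3.1.8 has two layers of adjusted Cox model. The primary multivariate model holds corneal diagnosis and binary preservation time, with no selection. The additional models consider further potential confounders, including "observations during or after cutting, time from cut to surgery, and donor rim culture results". Candidates are "screened by assessing the change in the preservation time effect" when each is controlled for, but no size of change is stated. Factors with univariate p<0.10 then go forward, and backward selection keeps those with p<0.01.

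Protocol 7.2.1.2 has the same change-in-effect screen with removal at P>0.05. It does not name these three variables; the SAP adds them.

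Other sections bear on the point:

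- **Protocol 2.6 and 3.1.2:** the eye is randomized, stratified by surgeon, and a donor is then assigned. "For those assignments where pre-cut tissue has been requested, the eye bank will cut and prepare" the tissue on the day it would have been cut for a non-study patient of the same surgeon.
- **Protocol 4.6:** "Additionally, data on donor tissue rim cultures may be collected if performed as part of standard" of care.
- **SAP 3.1.7:** the non-inferiority decision uses the unadjusted Kaplan-Meier difference.
- **SAP 8.3:** the 3-year methods carry over to years 4 and 5.

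**The concern.** A confounder of a randomized comparison has to be something that the allocated treatment cannot change. Here the treatment is storage time, and these three variables are recorded on tissue that is already in storage or has left it.

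Within a randomized comparison, a covariate shifts the estimated effect either through chance imbalance or because treatment altered it. A screen on change in effect cannot tell the two apart, so it can bring in a variable on the causal path. The model then estimates only the part of the storage effect that bypasses that variable, although 3.1.8 presents it as the confounder-adjusted effect.

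At stake is the reading of the secondary hazard ratios at 3 years and in the year 4 and 5 repeats. The SAP is careful elsewhere about bias towards non-inferiority: sections 3.1.2, 3.1.2.1 and 3.1.2.2 each justify a choice on that ground. This list could work in the opposite direction.

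**Working it through.** **1. The plan's own figure.** Inputs from Protocol 7.1 (repeated in SAP 2.0): 6% failure in both groups, 4-point margin, one-sided 5% error, 90% power, equal allocation.

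n per group = (1.6449 + 1.2816)² × 2 × 0.06 × 0.94 / 0.04² = 8.564 × 0.1128 / 0.0016 = 603.8, rounded up to 604. The total is 1208, as stated. Adding 10% gives 1208 × 1.10 = 1329, against the stated 1330. The sample size is not in question; it supplies 604 per group for the illustration below.

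**2. Hazard ratio for harm at the margin.** With 10% against 6% at 3 years, HR = ln(0.90)/ln(0.94) = 0.10536/0.06188 = 1.70.

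**3. Could storage affect these variables, on the plan's own terms?**

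| Variable | What the documents say | Consequence of storage? |
|---|---|---|
| Cutting observations | Made on tissue cut after assignment (Protocol 3.1.2). SAP 4.3 models another in-storage measure, pre-operative ECD, as an outcome of preservation time | Plausible |
| Rim culture result | SAP 5.0 lists endophthalmitis and corneal infection as possibly related to preservation time | Plausible |
| Cut-to-surgery time | A segment of preservation-to-surgery time, but the cutting day follows surgeon routine and randomization is stratified by surgeon | Less plausible; may differ little by group |

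SAP 4.1.4 expects no confounding by screening ECD because randomization should balance it. That reasoning protects factors fixed before storage. It does not protect variables that storage can alter.

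**4. Size, on assumed inputs.** Suppose one binary variable has prevalence q0 in the ≤7 day group and q1 in the 8 to 14 day group, and multiplies the failure hazard by h. For uncommon failure, approximately:

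adjusted HR ≈ 1.70 × [1 + q0(h − 1)] / [1 + q1(h − 1)]

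- 5% to 10%, h = 1.5: 1.70 × 1.025/1.05 = 1.66
- 5% to 10%, h = 3: 1.70 × 1.10/1.20 = 1.56
- 10% to 30%, h = 5: 1.70 × 1.40/2.20 = 1.08

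A simulation avoids the approximation and applies the p-value steps. It used 2,000 trials per scenario, 604 eyes per group, exponential failure times, true 3-year failure of 10% against 6%, no loss to follow-up, and a constant-hazard rate regression in place of Cox. A variable was kept if univariate p<0.10 and then adjusted p<0.01. Entries are the median preservation-time HR with the variable in the model, and in brackets the percentage of trials in which the rule kept it.

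| Prevalence, ≤7 d to 8–14 d | h = 1.5 | h = 2 | h = 3 | h = 5 |
|---|---|---|---|---|
| 5% to 5% (no storage effect) | 1.68 (9.4) | 1.72 (30.5) | 1.71 (76.7) | 1.73 (99.0) |
| 5% to 10% | 1.66 (13.7) | 1.62 (41.4) | 1.57 (88.7) | 1.48 (100) |
| 5% to 15% | 1.63 (14.6) | 1.56 (52.1) | 1.47 (93.9) | 1.31 (100) |
| 10% to 20% | 1.63 (20.1) | 1.57 (63.2) | 1.44 (98.8) | 1.35 (100) |
| 10% to 30% | 1.56 (21.5) | 1.45 (69.4) | 1.29 (98.9) | 1.10 (100) |

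Without the variable, the median HR was 1.67 to 1.72 throughout. Two things follow. First, the first row shows no attenuation, so the harm depends entirely on storage shifting the variable. Second, the p-value steps respond mainly to how strongly the variable predicts failure. They keep harmless and intermediate variables alike, so they do not create the bias but give no protection from it. The change-in-effect screen was not simulated, because the SAP gives no size of change.

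**The case against.** The strongest reply is that nothing decisive rests on these models. That is correct. SAP 3.1.7 decides non-inferiority on the unadjusted difference, and the primary multivariate model is already fixed in advance. The point is confined to the additional models.

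Second, the documents do not show that storage changes any of the three variables. This also stands: the direction is conditional and the size unknown. For cut-to-surgery time, the surgeon's routine and the stratification by surgeon argue against a difference between groups.

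Third, checking tissue processing is reasonable, because Protocol 3.1.2.1 lets tissue be imported when none in the window is available, so processing may differ by source. That is a good reason to look at these variables. It does not justify reading the adjusted coefficient as the effect of storage.

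Fourth, p<0.01 is stricter than the protocol's 0.05 and drops weak intermediates more often. True, but the strong ones remain.

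Two further inferences are tempting but not supported. One is that a model with rim culture must drop eyes selectively: Protocol 4.6 says only that results may be collected where culture is usual care, and the SAP does not specify complete-case analysis. The other is that the selection rule contradicts itself: a change-in-effect screen followed by p-value retention is a sequence that lacks a threshold, not a contradiction.

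**Conclusion.** The point holds for the additional models of SAP 3.1.8. Cutting observations, rim culture results and, less plausibly, cut-to-surgery time should not be screened as confounders of preservation time, because they arise after randomization and during or after storage. If storage worsens such a variable and the variable raises failure, these models understate harm.

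On the assumed inputs above, a true HR of 1.70 would appear as about 1.66 at the weak end and 1.10 at the most extreme setting, and would not move if storage leaves the variable alone. The prevalences and failure hazard ratios are assumptions; the documents give none.

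A reader might infer that the trial's non-inferiority conclusion, or all of its adjusted results, are compromised. The documents do not support that, since the unadjusted test and the diagnosis-adjusted model contain none of these variables. A reader might also infer that cutting takes place after most of the storage time has passed; no such interval is given.

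**What to change.** In SAP 3.1.8, limit confounder adjustment of the preservation-time effect to named recipient and donor factors fixed before storage, and delete the three variables from that list. Fixed before storage is the criterion to write down. Fixed before randomization would not work, because donors are chosen after the eye is randomized and donor age would then fail the test. The exact choice of factors is for the study team.

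Report any model containing cutting observations, cut-to-surgery time or rim culture as exploratory, and state that its preservation-time coefficient is not the total effect of storage. The same statement is needed in SAP 3.2.2, where the first two are already listed and preservation-time group is in every model. Rim culture is not listed there and would have to be added. The change should carry through to the extension analyses in SAP 8.3.

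The cost is minor rewording. The trade-off is that chance or sourcing differences in tissue processing are then examined only in exploratory models.
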